9.3. Medical History

Medical history will be collected only at screening and will be coded using Medical Dictionary for Regulatory Activities (MedDRA, Version 25.0, March 2022).

Medical history will be summarized by treatment group and period. The summary will include number and percentage of subjects reporting each system organ class (SOC) and preferred term (PT) and will be sorted alphabetically by SOC and descending frequency of PT within SOC in the Nemolizumab 30mg Q4W group. Summary tables will be presented for the ITT population.

Medical history data listings will be presented by subject number, period, start date, stop date, SOC, and PT for the ITT population.

9.4. Medical and Surgical Procedures

Medical and surgical procedures will be coded using MedDRA, Version 25.0, March 2022.

Prior medical and surgical procedures are defined as those which have been stopped before first treatment.

- Procedure before informed consent signed is defined as those stopped before the date of informed consent signed to the study.
- Procedure during screening period is defined as those stopped on or after the date of informed consent signed until before first treatment date.

Concomitant medical and surgical procedures will be defined as those started or stopped on or after the first treatment, or were ongoing during the study. If a procedure is started before the first treatment but ongoing or stopped on or after the first treatment, it will be considered concomitant.

This document is confidential.

- Procedures during treatment period are defined as those started, stopped, or ongoing during the period.
 - Procedure during Initial Period is defined if started or stopped or ongoing during Initial Period.
 - Procedure during Maintenance Period is defined if started or stopped or ongoing during Maintenance Period.
 - If early discontinued during Initial (or Maintenance) Period, the treatment period will be defined from start of treatment till 4 weeks after the last treatment or early discontinuation date whichever is earlier.
- Procedures during follow-up period are defined as those started, stopped, or ongoing during the period.
 - Follow-up Period is defined if used from post treatment period to follow-up visit date.
 - Procedure during Follow-up Period will be summarized in accordance with the respective period (Initial or Maintenance).
- If procedure is being used continuously during both periods (e.g., started in the Initial Period and ended or ongoing in the Maintenance Period), it will be counted for each period.

If the stop date and 'ongoing' are missing then the procedure will be considered concomitant. If stop date is partially missing, the procedure will be considered concomitant unless the non-missing part of date proves it ended prior to the first treatment date.

The following medical and surgical procedures (prior, concomitant and rescue procedures) will be summarized by treatment group and period using the number and percent of subjects reporting each SOC and PT and sorted alphabetically by SOC and descending frequency of PT within SOC in the Nemoalizumab 30mg Q4W group. Summary tables will be presented for the ITT population.

- Prior procedure before screening (before informed consent date)
- Prior procedure before first dosing (from screening [informed consent date] before the first treatment)
- Concomitant procedure during treatment period (initial and maintenance)
- Concomitant procedure during follow-up period
- Rescue procedure during treatment period (initial and maintenance)
- Rescue procedure during follow-up period

Medical and surgical procedures listings and rescue procedure listing will be presented by treatment group for ITT population and sorted by subject number, start date, stop date, SOC, and PT.

9.5. Medication

Medications will be classified and summarized on the ITT population as follows:

- Prior medications are defined as those which stop before the first injection of study drug during the study.
 - Prior medication before informed consent signed is defined as those stopped before the date of informed consent signed to the study.
 - Prior medication during screening period is defined as those stopped during screening period (on or after the informed consent date until before the first treatment date).
- Concomitant medications are defined as those started or stopped on or after the first injection of study drug.

This document is confidential.

- Medication during treatment period are defined as those started, stopped, or ongoing during the period.
 - Medication during Initial Period is defined if started or ongoing or ended during Initial Period.
 - Medication during Maintenance Period is defined if started or ongoing or ended during Maintenance period.
 - If early discontinued during Initial (or Maintenance) Period, the treatment period will be defined from start of treatment till 4 weeks after the last treatment or early discontinuation date whichever is earlier.
- Medication during follow-up period are defined as those started, stopped, or ongoing during the period.
 - Follow-up Period is defined from post treatment period to follow-up visit date.
 - Medication during Follow-up Period will be summarized in accordance with the respective period (Initial or Maintenance).
- If medication is being used continuously during both periods (e.g., started in the Initial period and ended or ongoing in the Maintenance period), it will be counted for each period.

If the stop date and 'ongoing' are missing then the medication will be considered as concomitant medication. If stop date is partially missing, the medication will be considered as concomitant unless the non-missing part of date proves it ended prior to the first treatment date.

Medications (prior, concomitant and rescue medications) will be coded using Version B3 March 2022 of the World Health Organization's Drug Dictionary (WHO DD). Preferred Anatomical Therapeutic Chemical (ATC) coding will be performed.

The following summaries by ATC level 2, ATC level 4 and preferred term (PT) will be produced on the ITT population. Subjects with more than one medication in a given ATC level and preferred name will be counted only once in that category. It will be sorted ATC level alphabetically and descending frequency in PT within ATC level term.

- Prior medication before screening (before informed consent date)
- Prior medication before first dosing (from screening [informed consent date] before the first treatment)
- Concomitant medication during treatment period (initial and maintenance)
- Concomitant medication during follow-up period
- Rescue medication during treatment period (initial and maintenance)
- Rescue medication during follow-up period
- Background topical therapy (TCI/TCS) during treatment period (initial and maintenance)
- Background topical therapy (TCI/TCS) during follow-up period

All medications (prior and concomitant medications, rescue medications, background TCI/TCS will be listed for the ITT population. In addition background TCI/TCS dispensation and receipt will be listed for the ITT population.

9.6. Extent of Exposure

The extent of exposure will be summarized for the Initial Period and the Maintenance Period. Summary for Overall Treatment Period (from Initial to Maintenance Period) will be included in the Maintenance Period summary table.

This document is confidential.

The number of subjects exposed will be summarized for the Initial Period and Maintenance Period, and Overall Period (Initial + Maintenance).

- Treatment duration (in days) is calculated as follows, where date of first treatment is defined as the first day of the relevant study Period: [(date of last treatment – date of first treatment) + 1].
- Total number of doses administered will be calculated as the sum of all doses of study drug administered.
- Total number of doses planned will be calculated as the sum of all doses of study drug planned (dispensed) according to the treatment schedule of the treatment group. If a subject missed dosing due to skipped visit or completed a visit without dosing, this missed dose which is supposed to be dispensed will be accounted for the calculation.
- The number of subjects who missed at least one dose
- The number of subjects who missed at least one dose due to COVID-19*
- The number of doses missed
- The number of doses missed due to COVID-19*

**The reason for dose not administered reported in CRF is COVID-19 [This will be identified using Other specify field in CRF].*

9.7. Treatment Compliance

Treatment compliance will be assessed through the treatment records and drug dispensation logs. As study drug is administered in the clinic, treatment compliance will be overseen and documented by the investigator and study staff (using the treatment records and drug accountability records).

Treatment compliance(%) will be calculated by Period as total number of actual injections/ total number of expected injections*100.

This document is confidential.

10. Efficacy

The ITT population will be the primary population for all efficacy analyses. Both primary and key secondary and secondary endpoints of the Initial Period will be analyzed for the following populations:

- Full population which includes all subjects in ITT population
- Baseline PP NRS ≥ 7

All efficacy variables will be summarized by treatment group at each analysis visit, separately for the Initial Period and Maintenance Period. The primary comparison of interest is nemolizumab 30 mg compared to placebo for the co-primary endpoints in both populations (Full population; Baseline PP NRS ≥ 7).

To control the type I error at 5% significance level, a serial gatekeeping approach will be implemented. The co-primary endpoints will be tested at 2.5% significance level for each population. If both co-primary endpoints are statistically significant at 2.5% significance level, the key secondary endpoints will be tested sequentially following hierarchical testing procedure using the pre-specified order of endpoints for each population. The comparisons for key secondary endpoints will be made sequentially, and the subsequent tests will be stop when no statistical difference is found.

If $p < 2.5\%$ for all endpoints (co-primary and key secondary) in at least one population, then 2.5% will be recycled to test other population at 5% level of significance.

Other secondary endpoint comparisons will not be adjusted for multiplicity.

10.1. Primary Efficacy Endpoints and Analysis

10.1.1. Primary Analysis of Primary Efficacy Endpoint

Primary efficacy endpoint consists of the two co-primary endpoints:

- Proportion of subjects with an IGA* success (defined as an IGA of 0 [clear] or 1 [almost clear] and a ≥ 2 -point reduction from Baseline) at Week 16
- Proportion of subjects with EASI-75* ($\geq 75\%$ improvement in EASI from Baseline) at Week 16

* Further details regarding IGA and EASI-75 can be found in Sections 10.3.1 and 10.3.2 respectively.

Assessment results after taking rescue medication will be considered as treatment failure i.e. non-responders. Missing values at Week 16 will be treated as non-responder.

Both co-primary endpoints will be analyzed using a Cochran-Mantel-Haenszel test adjusted for the randomized stratification variables (IGA severity [3=moderate, 4=severe] and PP NRS [≥ 7 , < 7] for full population; IGA severity only for Baseline PP NRS ≥ 7 population) at 2.5% significance level (2-sided). In addition an unadjusted CMH test will be performed.

The proportion of subjects with IGA success and with EASI-75 at Week 16 will be summarized. The estimate of treatment unadjusted difference with the corresponding 2-sided 95% confidence interval and strata-adjusted difference with the corresponding 2-sided 97.5% confidence interval, and p-values will be presented.

Bar charts for the proportions of subjects with IGA success and subjects with EASI-75 at Week 16 will be presented.

This document is confidential.

In addition, the proportion of subjects with IGA success will be analyzed using non-responder imputation on the ITT population excluding subjects who used the different version of IGA.

Additional summary tables for primary endpoints will also be presented by visit but excluding subjects from the visit summarized if the visit was affected by pandemic.

10.1.2. Sensitivity Analyses of Primary Efficacy Endpoint

The following sensitivity analyses for both populations will be conducted for the robustness of the primary analyses.

- Same analysis on PP population
- Tipping point analysis (see Appendix 22.1)
- Multiple imputation (MI) methods (see Appendix 22.1)
- Last Observation Carried Forward (LOCF) imputation method for missing data. Missing post-baseline values will be carried forward from the last non-missing post-baseline value. Baseline value will not be carried forward to post-baseline value.
- Observed Case (OC) - no data will be imputed. For this analysis, if any rescue medication is received, data post-rescue therapy will be analyzed as observed (i.e., not considered treatment failure).
- Same analysis on ITT using 'actual stratum' instead of 'stratum at the randomization'.

Tipping point analysis, multiple imputation methods, LOCF and OC analysis will be performed on the ITT population. Except OC analyses, assessments on or after rescue therapy used will be considered as treatment failure and will be considered as non-responders for analysis.

10.1.3. Subgroup Analyses of Primary and Key Secondary Efficacy Endpoints

In addition, the same analyses as described in Section 10.1.1 (with strata-adjusted 95% CI instead of strata-adjusted 97.5% CI) will be performed for the subgroups defined in Section 8.6.

[figure not shown]
The subgroup analyses will be performed on the ITT population (Full population; Baseline PP NRS ≥ 7) for primary and key secondary endpoints. Forest plot will be presented along with subgroup analysis results.

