8.1. General Methods

All data will be listed, and summary tables will be provided. Summaries will be presented for each treatment and visit (if applicable).

Unless otherwise stated, continuous variables will be summarized using the number of observations (n), mean, standard deviation (SD), median, Q1, Q3, minimum, and maximum by treatment group and visit (if applicable). Categorical variables will be summarized using frequency and percentages of subjects for each category by treatment group and visit (if applicable).

Unless otherwise stated, all statistical tests will be 2-sided and conducted at the 5% level; all presented confidence intervals (CIs) will be 2-sided 95% CIs.

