8.6. Subgroups

Descriptive summary and analysis for primary and selected key secondary endpoints will be produced for the following subgroups:

- Region (Europe, North America, Asia Pacific)
- Age groups (12-17, 18-65, and > 65)
- Sex
- Race
- Baseline IGA (3 or 4)
- Baseline PP NRS (≥ 7 and < 7)
- Previous use of any systemic therapy for AD (Yes, No)
- Previous use of any biologic therapy for AD (Yes, No)
- Previous use of any immunosuppressive or immunomodulatory drugs for AD (Yes, No)
- Previous use of Dupilumab for AD (Yes, No)
- Previous use of Cyclosporine for AD (Yes, No)
- Country

This document is confidential.

9. Demographic, Other Baseline Characteristics and Medication

Subject accounting, disposition, demographics, Baseline characteristics, previous therapies, and concomitant therapies by treatment will be summarized for the Initial Period and Maintenance Period.

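### Subgroup tables test the drug effect separately in each level, but the readable plan never tests whether the effect differs between levels, so small levels may look like non-responding groups through size alone.

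*SAP*

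**What the plan says.** SAP 10.1.3 states that "the same analyses as described in Section 10.1.1 (with strata-adjusted 95% CI instead of strata-adjusted 97.5% CI) will be performed for the subgroups" listed in 8.6, in both populations, "for primary and key secondary endpoints. Forest plot will be presented along with subgroup analysis results". The analysis carried over from 10.1.1 is a stratified CMH test "at 2.5% significance level (2-sided). In addition an unadjusted CMH test will be performed", with differences, confidence intervals and p-values. SAP 10.2 extends the same scheme to the key secondary endpoints, of which the title of Table 7-3 counts nine.

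Section 8.6 lists 12 factors, among them age group, race, country, baseline PP NRS and five prior-therapy factors. Its scope differs from that of 10.1.3: "Descriptive summary and analysis for primary and selected key secondary endpoints will be produced for the following subgroups".

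The level at which subgroup tests are read is not explicit. Section 10.1.1 gives 2.5%. The default in 8.1 is that "all statistical tests will be 2-sided and conducted at the 5% level", and 10.1.3 moves the strata-adjusted interval to 95%.

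The gatekeeping in SAP Section 10 covers the co-primary and key secondary endpoints in the two populations. The only sentence about unadjusted testing is "Other secondary endpoint comparisons will not be adjusted for multiplicity", and it does not mention subgroups.

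**The concern.** The question for a subgroup analysis is whether the treatment effect differs between levels. A p-value computed inside one level answers something else: whether that level alone is large enough to detect an effect. When the effect is the same everywhere, large levels come out significant and small ones often do not, and the table then reads as if the drug failed in the small ones.

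Adolescents, subjects over 65, prior-biologic users and single countries are the levels most exposed, and conclusions about labelling or use could be drawn from them.

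The comparison with most weight is PP NRS <7 against >=7. Protocol 8.2.1 explains that the phase 2b population had PP NRS >=7 and that this trial lowered the threshold to 4. The full-population result supports that extension only if there is benefit below 7. The readable text tests the full population and the >=7 population, and shows the <7 stratum as a subgroup row, but does not test the difference between strata.

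**Working it through.** **Inputs.** IGA success 30% vs 12% and EASI-75 49% vs 19%; 750 subjects randomized 2:1; at least 250 per PP NRS stratum (SAP 4.1, 4.3). At least 130 adolescents (protocol 8.3.1). Dropout 15% (protocol 10.2). Other level sizes below are assumptions. Missing values count as non-response, so randomized numbers are used in the subgroup figures.

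**Formula.** Two-sided test of two proportions, a stand-in for CMH:

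power = Φ[(d − z·s0)/s1], with s0 = √[p̄(1−p̄)(1/nN + 1/nP)] and s1 = √[pN(1−pN)/nN + pP(1−pP)/nP], where N is nemolizumab and P placebo; z = 1.960 at 5% and 2.241 at 2.5%.

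**1. The plan's own figure.** IGA, 500 vs 250, 2.5%: s0 = 0.0331, s1 = 0.0290; (0.18 − 2.241×0.0331)/0.0290 = 3.65, power 99.99%. After 15% dropout (425 vs 212.5) it is 99.92%. EASI-75 is about 100%. The stated power of more than 99% is reproduced.

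**2. Power inside one level, same true effect everywhere.** For 130 adolescents (86.7 vs 43.3), IGA: s0 = 0.0795, s1 = 0.0697.
- At 5%: (0.18 − 1.960×0.0795)/0.0697 = 0.35, power 0.64.
- At 2.5%: (0.18 − 2.241×0.0795)/0.0697 = 0.03, power 0.51.

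| Level size | IGA 5% | IGA 2.5% | EASI-75 5% | EASI-75 2.5% |
|---|---|---|---|---|
| 250 | 0.91 | 0.85 | 1.00 | 1.00 |
| 130 | 0.64 | 0.51 | 0.94 | 0.89 |
| 90 (assumed) | 0.47 | 0.34 | 0.81 | 0.72 |
| 75 (assumed) | 0.39 | 0.28 | 0.73 | 0.62 |
| 45 (assumed) | 0.24 | 0.15 | 0.49 | 0.37 |

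With an assumed age split of 130/580/40, the IGA powers at 5% are 0.636, 0.999 and 0.211. The chance that at least one age level is non-significant, with no heterogeneity at all, is 1 − 0.636×0.999×0.211 = 0.87.

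**3. Full-population IGA test with zero effect below PP NRS 7.** With n7 subjects at >=7, the nemolizumab rate is 0.12 + 0.18×n7/750. The two stratum minimums allow n7 from 250 to 500. At 2.5%:
- n7 = 250: 18% vs 12%; (0.06 − 2.241×0.0284)/0.0268 = −0.14, probability 0.45.
- n7 = 375: 21% vs 12%; (0.09 − 2.241×0.0298)/0.0275 = 0.84, probability 0.80.
- n7 = 500: 24% vs 12%; (0.12 − 2.241×0.0310)/0.0281 = 1.80, probability 0.96.

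These are for IGA alone; the co-primary criterion also requires EASI-75.

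**4. What an interaction test would deliver.** Power = Φ(|d1 − d2|/SE − 1.96), with SE² the sum of the two levels' s1².
- PP NRS <7 vs >=7, effect 0 vs 18 points, n7 = 250/375/500: SE 0.0590/0.0543/0.0563, power 0.86/0.91/0.89.
- Adolescents vs the rest (130 vs 620), 9 vs 18 points: SE 0.0733, power 0.23. With 0 vs 18 points: SE 0.0684, power 0.75.
- Twelve independent 5% tests under no heterogeneity: 1 − 0.95^12 = 0.46 chance of at least one false positive.

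**The case against.** The strongest reply is that subgroup rows are supportive. They sit outside the alpha scheme, 8.6 uses the word descriptive, and estimates, 95% CIs and forest plots per level are already planned. All of that stands. The switch to a 95% interval also suggests 5% rather than 2.5% as the level for reading subgroups, so 64% is the fairer adolescent figure, and EASI-75 is much less exposed than IGA.

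On PP NRS, the planned <7 row would itself be informative. With 250 subjects and 12% response in both arms, the standard error is √[0.12×0.88×(1/167 + 1/83)] = 0.044 and the interval about ±8.5 points. Its upper limit would fall below 18 points in about 98% of trials. That covers a total absence of effect, but it remains an interval for one stratum and not a comparison of two.

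A reader might go further and infer any of the following:
- That chance positives and low-power negatives are both likely. They need opposite truths: under the planned effect a significant level is a true positive, and chance positives matter only where there is no effect.
- That all 11 endpoints (2 + 9) are covered. Section 8.6 limits the key secondary endpoints to a selection, so 11 is an upper bound from 10.1.3 and 10.2.
- That no subgroup level has multiplicity control. The PP NRS >=7 level is a formally tested population.
- That no interaction test exists anywhere. Section 10.1.3 has an omitted figure and 10.2 has redacted text, so the statement holds for readable text only.

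**Conclusion.** The point holds as a limited but worthwhile improvement. The readable SAP plans CMH p-values inside each subgroup level, in both populations, and no test of whether effects differ between levels. It does not say explicitly how those p-values are to be used; the word descriptive in 8.6 is attached to a phrase that also promises analysis.

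The main risk is false apparent heterogeneity: for IGA, a 36% (5%) to 49% (2.5%) chance that 130 adolescents come out non-significant when they benefit exactly as everyone else does. The second gap is the missing PP NRS comparison, with a 0.45 to 0.96 chance of a significant full-population IGA test if there is no effect below 7.

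The documents do not support reading this as a threat to the trial's type I error. The confirmatory hierarchy is untouched.

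The figures rest on the plan's response rates and a normal approximation in place of stratified CMH. Only the 130 adolescents and the 250 per PP NRS stratum are documented level sizes.

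**What to change.** In SAP 10.1.3:
- Report the strata-adjusted difference and 95% CI per level, as already planned, and remove the level-specific significance tests.
- Add one nominal treatment-by-subgroup p-value per factor, for example a homogeneity test of the level-specific risk differences. Show the one for PP NRS <7 vs >=7 beside the full-population co-primary result.
- State that all subgroup results, interaction tests included, are exploratory.
- Omit the baseline PP NRS factor from the PP NRS >=7 tables, where the <7 row is empty apart from any mis-stratified subjects.

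Reconcile the endpoint scope in 8.6 with 10.1.3 and 10.2, so that one list applies.

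The cost is a few sentences and one changed column in the forest-plot tables; no primary result changes. The downside is the low power of interaction tests in small levels (23% for a halved adolescent IGA effect) and the 46% chance of a stray positive over twelve independent tests. The text should therefore say that a non-significant interaction does not prove consistency and that a single significant one supports no claim.
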